## **1.2 Schedule of Assessments – Prior to Study Virtualization**

**1.3 Schedule of Assessments – Following Study Virtualization**

Study Period	Treatment Period										EOT 	EOS  / ET	F/U	USV 3,4
Visit Number		RV1	TC1	RV2	TC2	RV3	TC3	RV4	TC4	RV5	RV	RV	TC	RV/ TC
Study Procedures and Assessments	VTV	Within 30 days of VTV	Week 13 (±14 days)	Week 26 (±14 days)	Week 39 (±14 days)	Week 52 (±14 days)	Week 65 (±14 days)	Week 78 (±14 days)	Week 91 (±14 days) and every 13 weeks (±14 days) thereafter	Week 104 (±14 days) and every 26 weeks (±14 days) thereafter	Week X (±Y days)	Week X (±Y days)	Week X (±30 days)	Week X (±Y days)
Remote Visit		X		X		X		X		X	X	X		X
Telephone Contact			X		X		X		X				X	X
Informed Consent 	X													X 
Designation of Research Proxy	X													
Updated Medical History	X 													
Eligibility Criteria	X	X												
Evaluation for Research Study Consent	X	X	X	X	X	X	X	X	X	X	X	X	X	X
Test Connection 	X													
Mobile Device Kit	X											X		
Training Review	X													
Concomitant Medication Inquiry	X	X	X	X	X	X	X	X	X	X	X	X	X	X
Benzodiazepines and Antidepressants Inquiry 	X	X	X	X	X	X	X	X	X	X	X	X	X	X
Alcohol/Illicit Drug use Inquiry	X	X	X	X	X	X	X	X	X	X	X	X	X	X
Physical Exam	X													
Weight	X	X		X		X		X		X	X	X		X
Vital Signs (HR, BP) 	X	X		X		X		X		X	X	X		X
12-lead ECG 	X	X		X		X		X		X	X	X		X
Pregnancy Test 	X	X				X				X	X	X		X
Safety Laboratory Tests 	X	X		X		X		X		X	X	X		X
Creatinine Clearance Calculation 	X	X		X		X		X		X	X	X		X
UHDRS 	X	X				X				X	X	X		X
AE Review	X	X	X	X	X	X	X	X	X	X	X	X	X	X

Study Period	Treatment Period										EOT 	EOS  /ET	F/U	USV 3,4
	Visit Number	RV1	TC1	RV2	TC2	RV3	TC3	RV4	TC4	RV5				
Study Procedures and Assessments	VTV	Within 30 days of VTV	Week 13 (±14 days)	Week 26 (±14 days)	Week 39 (±14 days)	Week 52 (±14 days)	Week 65 (±14 days)	Week 78 (±14 days)	Week 91 (±14 days) and every 13 weeks (±14 days) thereafter	Week 104 (±14 days) and every 26 weeks (±14 days) thereafter	Week X (±Y days)	Week X (±Y days)	Week X (±30 days)	Week X (±Y days)
C-SSRS 	X	X	X	X	X	X	X	X	X	X	X	X	X	X
Abbreviated PBA-s 			X	X	X		X	X	X				X	
Satisfaction Survey 		X		X		X		X		X	X			
Dispense IMP and Instructions 	X			X	X	X	X	X	X	X				X
IMP Accountability 	X	X		X		X		X		X	X 	X 		
IMP Compliance	X	X	X	X	X	X	X	X	X	X	X	X		X

 This visit will be undertaken in place of the Early Termination visit when a patient is no longer able to receive IMP for various reasons but wishes to remain in the study. Patients who discontinue IMP due to safety or tolerability reasons, or the inability to complete virtual visits, may remain enrolled in the study without treatment at the discretion of the investigator (or qualified designee). Patients should complete the EOT visit and continue with scheduled visits and assessments until the EOS or ET. For subsequent visits, these patients will follow the Schedule of Assessments for the remaining remote video/mobile nurse and safety evaluation telephone contact visits.

 EOS is defined as the last visit of the last patient. All devices will be returned to the investigational center or vendor at the end of the study.

 An USV may be performed at any time during the study as deemed necessary by the investigator (or qualified designee). The date and reason for an USV will be recorded. Reasons for USVs may include, but are not limited to, need for blood draw for safety labs, a potential severe side effect, worsening of symptoms, etc. The following assessments are required at an USV: AE review and concomitant medication inquiry. Other assessments to be done at the discretion of the investigator (or qualified designee). The primary form of contact will be a TC, but video assessments and in-person visits may be scheduled at the discretion of the investigator (or qualified designee).

 For patients with concerns about the virtual nature of site visits, 1 site USV per year may take place at the investigational site that follows the assessments required for the safety evaluation TCs. The medical monitor will review individual requests for site visits and approve visits if deemed necessary. The investigator (or qualified designee) may schedule additional site visits on a case-by-case basis for patients that require closer monitoring due to safety events.

 Patients will complete the informed consent at their last in-person Open-HART study visit/VTV.

 An USV may also be scheduled to re-consent patients (if necessary).

 Medical history collected prior to study virtualization will remain in a separate database while updated medical history will be collected at VTV.

 Test connections are to be completed at home (and/or applicable location) by the vendor prior to the first remote visit to ensure remote video conferencing equipment functionality.

 Information on benzodiazepines and antidepressants will be collected as part of the concomitant medication inquiry.

 The mobile nurse will complete the collection of safety laboratory tests, measurement of ECGs, and vital signs at home (and/or applicable location).

 Vital signs measurements include HR, BP, and weight.

- 
-  ECGs will be performed every 6 months unless a safety signal is detected. If a safety signal is detected, the mobile nurse will measure ECGs every 3 months. An ECG safety signal is defined as a QTcF  $\geq 480$  ms and  $\leq 500$  ms ( $\geq 60$  ms increase from VTV).
-  Urine pregnancy tests are to be performed as applicable based on gender and menopausal status. Serum pregnancy tests must be used to confirm a positive urine pregnancy test result.
-  Safety laboratory tests include potassium, magnesium, calcium, and creatinine clearance.
-  Creatinine clearance will be calculated using the Cockcroft-Gault equation. Patients that de-escalate to half-doses of IMP will have creatinine clearance monitored more frequently than patients at the full dose, as determined by the investigator (or qualified designee).
-  UHDRS includes Motor Assessment, Cognitive Assessment (Stroop Interference, Verbal Fluency, and Symbol Digit Modalities Test), Behavioral Assessment, Functional Assessment, Independence Scale, Total Functional Capacity, and Summary sections. UHDRS Motor exam will be modified as portions will be considered "unable to rate" (such as rigidity, tandem walking, and retropulsion pull test tasks).
-  The C-SSRS "Since Last Visit" version will be utilized at all visits. If the patient scores  $>2$  on the C-SSRS for suicidal ideation, the safety TCs should be performed monthly or bi-monthly per investigator (or qualified designee) judgement.
-  The safety TCs and remote visits will include an abbreviated PBA-s assessment (a subset of PBA-s questions on depressed mood, suicidal ideation, anxiety, irritability, loss of motivation, and obsessive-compulsive behaviors) when the UHDRS is not completed.
-  Separate Satisfaction Surveys will be administered to patients and investigators (or qualified designees).
-  Dispensing of IMP after the VTV will occur as direct-to-patient shipments at approximately 13-week intervals.
-  The mobile nurse will perform IMP accountability at each home visit. IMP (unused and used packaging) will be collected by mobile nurses at each mobile nurse visit and shipped back to the distributor. All unused IMP will be returned.
- Abbreviations: AE=adverse event; BP=Blood Pressure; C-SSRS=Columbia-Suicide Severity Rating Scale; ECG=electrocardiograph; EOS=End of study; EOT=End of treatment; ET=Early termination; F/U=Follow-up visit; HR=Heart Rate; PBA-s=Problem Behaviors Assessment-Short Form; QTcF= QT interval corrected for heart rate using Fredericia's formula; RV=Remote visit; TC=Telephone contact; UHDRS=Unified Huntington's Disease Rating Scale; USV=Unscheduled Visit; VTV=Virtual Transition Visit.

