#### **5.3.1 Dose Frequency Reduction**

In the event of tolerability problems, patients will be instructed to immediately contact their investigator (or qualified designee) to discuss their AEs. The investigator (or qualified designee) will assess whether or not the AEs could be related to IMP and severe enough to warrant a dose frequency reduction. The patients will be instructed to stop taking 1 of the 2 capsules of their daily dose. Arrangements for an USV at the earliest opportunity will be made (see Section 4.6.5). At this visit patients will be provided with instructions regarding the de-escalated dose frequency. Alternatively, patients may be temporarily off drug up to 60 days per year in the event of tolerability problems, as judged by the investigator (or qualified designee).

---

IMP re-introduction or dose frequency increase back to the previous dose frequency may be considered if the clinical monitor, investigator (or qualified designee), and the patient agree that this should be attempted. Alternatively, qd dosing may be maintained.

Patients should be advised that if tolerability problems continue then they should contact their investigator (or qualified designee) who may then withdraw them from IMP (see Section 7.7.2 for withdrawal procedures).

IMP must be reduced to 45 mg qd for the following events:

- Any QTcF increase >60 ms from the first remote visit
- QTcF  $\geq$ 480 ms and  $\leq$ 500 ms
- Creatinine clearance <60 mL/min and >40 mL/min

If an IMP must be reduced to 45 mg qd and the patient is not currently at a study visit arrangements for an USV at the earliest opportunity will be made (see Section 4.6.5). At this visit, patients will be provided with instructions regarding the de-escalated dose frequency.

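### Protocol 1.3 footnote 12 and Section 5.3.1 define the QTcF trigger differently, so a patient can be dose-reduced for QTcF yet stay on 6-monthly scheduled ECGs

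*Protocol*

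**What the plan says.** Footnote 12 in Protocol 1.3 (schedule following virtualization) sets the ECG frequency: "ECGs will be performed every 6 months unless a safety signal is detected". It goes on to the closer schedule and the definition: "If a safety signal is detected, the mobile nurse will measure ECGs every 3 months. An ECG safety signal is defined as a QTcF" of at least 480 and at most 500 ms. A rise of at least 60 ms follows in parentheses, described as a "ms increase from VTV". No conjunction links the band to the rise.

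Section 5.3.1 states "IMP must be reduced to 45 mg qd for the following events" and lists the QTcF events as separate bullets: "Any QTcF increase >60 ms from the first remote visit" and "QTcF $\geq$ 480 ms and $\leq$ 500 ms".

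Other sections bear on the same readings:

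- **Section 6.2** takes a patient off IMP for QTcF above 500 ms or a rise above 60 ms from VTV. The patient may stay in the study off IMP, and an ECG follows in 4 weeks.
- **Sections 7.7.1 and 7.7.2** use those same two criteria to discontinue the patient from the study, also with an ECG in 4 weeks.
- **Section 6.2** also makes a VTV QTcF above 450 ms exclusionary, so values up to 450 ms are eligible.
- **SAP 2.1** says the SAP is based on Amendment 04 and that Amendment 05, the virtualization amendment, was issued but not implemented.

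**The concern.** Footnote 12 decides whose scheduled ECGs become more frequent, and Section 5.3.1 decides whose dose frequency is cut. Both use the 480-500 ms band and a change of about 60 ms, but they combine them differently, measure the change from different visits and use different inequalities. A reading serious enough to force a dose reduction may therefore leave the ECG schedule unchanged.

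Nothing else in the protocol closes this gap by rule. A reduction under 5.3.1 leads to an unscheduled visit, but Section 4.6.5 requires only adverse event review and a concomitant medication inquiry there, and telephone is the primary form of contact. Footnote 15 ties more frequent creatinine clearance checks to de-escalation, but no section does the same for ECGs. Section 2.3 describes the QTc effect as dose- and exposure-dependent, and Section 8.9.3 names QTcF as a safety parameter to be summarized, so the timing of these ECGs affects both patient safety and the safety data.

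**Working it through.** The protocol gives no figure to reproduce. The check sets the rules side by side and applies them to whole-millisecond values.

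| Rule | Band | Change | Reference | Link |
|---|---|---|---|---|
| Footnote 12: 3-monthly ECGs | 480-500 ms | ≥60 ms | VTV | not stated |
| 5.3.1: dose-frequency reduction | 480-500 ms | >60 ms | RV1 | either alone |
| 6.2: stop IMP | >500 ms | >60 ms | VTV | either alone |
| 7.7.1, 7.7.2: leave the study | >500 ms | >60 ms | VTV | either alone |

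**Parenthesis read as *and*.**

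- Take VTV = RV1 = 440 ms and a current value of 485 ms. The rise is 485 - 440 = 45 ms. Section 5.3.1 applies because 485 is in the band. Section 6.2 does not, because 485 ≤ 500 and 45 ≤ 60. Footnote 12 is not met, because 45 < 60. The dose is reduced and ECGs stay 6-monthly.
- For a VTV value of 441 ms, the largest rise inside the band is 500 - 441 = 59 ms, and for 450 ms it is 500 - 450 = 50 ms. No patient at 441-450 ms can meet the signal. The highest VTV value that can is 440 ms, since 500 - 440 = 60.
- Take VTV values of 380-450 ms, RV1 = VTV, and on-study values from the VTV value up to 520 ms. A cell has a 5.3.1 reduction and no 6.2 stop when the value is 480-500 ms and the rise is at most 60 ms. At 480 ms that admits VTV 420-450 (31 cells), falling by one per millisecond to VTV 440-450 at 500 ms (11 cells). The total is 21 × (31 + 11)/2 = 441 cells. Footnote 12 is met only where the rise is exactly 60 ms, which is 21 cells. The other 441 - 21 = 420 miss it.
- These cells map the rules; they are not patient frequencies.

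**Parenthesis read as *or*.**

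- With RV1 = VTV, all 441 cells meet the signal and the gap closes.
- With RV1 below VTV it reopens. Take VTV 380, RV1 370 and a current value of 431 ms. The rise from RV1 is 61 ms, so 5.3.1 applies. The rise from VTV is 51 ms, so neither footnote 12 nor 6.2 applies.
- With RV1 10 ms below VTV, 405 grid cells have a reduction, no stop and no signal. With RV1 10 ms above VTV, none do.

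**Rises above 60 ms from VTV.** If the rise from RV1 is also above 60 ms, 5.3.1 reduces the dose frequency, 6.2 stops IMP, and 7.7.1 and 7.7.2 end participation. These rules conflict with each other, whatever footnote 12 means.

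**The case against.** The strongest objection is that the text was never used. SAP 2.1 says Amendment 05 was not implemented, and its account of Amendment 04 has ECGs at the safety visits (3, 9, 15 months) and the clinic visits (6, 12, 18 months), so about every 3 months. This stands: the fault is confined to the Amendment 05 protocol text.

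Second, footnote 12 is ambiguous rather than plainly conjunctive. This also stands. A reader might infer that eligible patients nearest the 450 ms limit can never trigger closer monitoring, but that holds only under *and*. It is the natural reading, since the parenthesis directly qualifies the band, but the footnote does not state it. Ambiguity does not remove the problem, because a gap remains under *or*.

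Third, a reader might infer that patients with a rise above 60 ms and a value below 480 ms are simply left on 6-monthly ECGs. The documents do not support that when the rise is from VTV: 6.2, 7.7.1 and 7.7.2 then apply, each with an ECG in 4 weeks.

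Fourth, investigators may add ECGs or site visits at their discretion, and the schedule marks an ECG in the unscheduled-visit column. That mitigates the gap but does not close it, because the ECG is optional.

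Finally, a monitoring trigger narrower than the dose-reduction trigger could be deliberate. No section says the two must coincide, so the documents do not support requiring one list of events to drive both. If the difference is intended, the protocol should say so.

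**Conclusion.** The inconsistency is real. Footnote 12 and Section 5.3.1 differ on conjunction, inequality and reference visit. Under either reading, some patients whose dose frequency must be cut for QTcF keep 6-monthly scheduled ECGs. The clear case is a value of 480-500 ms with a rise below 60 ms, under *and*. Under *or*, the gap is limited to patients whose RV1 value lies below their VTV value.

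The gap follows from the rules by arithmetic, but its frequency cannot be established from the documents. A reader might want a percentage. As an illustration, assume VTV QTcF with mean 410-420 ms and SD 18 ms truncated at 450 ms, and an on-study change with SD 25 ms. The share of readings at 480-500 ms with a rise below 60 ms is then about 1.1% to 5.8% for a mean change of 10-30 ms, and about 0.6% to 1.2% for a mean change of zero. None of these inputs comes from the protocol or SAP, so the percentages should not be relied on.

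Practical weight is limited because Amendment 05 was not implemented. The text should still be corrected before any use of that version.

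**What to change.** Reconcile footnote 12 with Sections 5.3.1, 6.2, 7.7.1 and 7.7.2. The revised wording should state:

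- whether the band and the rise in footnote 12 are joined by *and* or *or*;
- whether the change criterion is above 60 ms or at least 60 ms;
- whether the change is measured from VTV or RV1;
- which ECG schedule applies to a patient whose dose frequency is reduced for QTcF;
- which of the conflicting actions in 5.3.1, 6.2, 7.7.1 and 7.7.2 applies to a rise above 60 ms.

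The sponsor decides the thresholds, the actions and the monitoring rule. The cost is protocol wording and, depending on that decision, at most a few additional nurse ECGs of a kind the protocol already provides for.

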#### 1.4 List of Abbreviations

AE	Adverse Event
bid	Twice Daily
CFR	Code of Federal Regulations
CI	Confidence Interval
C max	Maximum Concentration
CMSU	Clinical Materials Services Unit
CRO	Contract Research Organization
C-SSRS	Columbia-Suicide Severity Rating Scale
CTCC	Clinical Trials Coordination Center
CYP2D6	Cytochrome P450 2D6
D2R	Dopamine D2 Receptor
DSMB	Data Safety Monitoring Board
DSM-IV-TR	Diagnostic and Statistical Manual – Fourth Edition – Text Revision
DTP	Direct-to-patient
EC	Ethics Committee
ECG	Electrocardiogram
eCRF	Electronic Case Report Form
EDC	Electronic Data Capture
EM	Extensive Metabolizers
EOS	End of Study
EOT	End of Treatment
ET	Early Termination
FDA	Food and Drug Administration
F/U	Follow-up
GCP	Good Clinical Practice
HART	ACR16C009: A Multi-center, Randomized, Double-blind, Parallel-group Study Comparing Three Doses of ACR16 Versus Placebo for the Symptomatic Treatment of Huntington’s Disease. IND: 77,419.
HD	Huntington’s Disease
HDPE	High-density Polyethylene
HSG	Huntington Study Group
HTT	Huntingtin Gene
IB	Investigator’s Brochure
IC50	Half Maximal Inhibitory Concentration
ICF	Informed Consent Form
ICH	International Council on Harmonisation
ID	Identification
IMP	Investigational Medicinal Product
IND	Investigational New Drug
IRB	Institutional Review Board
IRT	Interactive Response Technology
MermaiHD	ACR16C008: A Multi-center, Multi-national, Randomized, Double-blind, Parallel-group Study Comparing ACR16 45 mg Once-daily or Twice-daily Versus Placebo for the Symptomatic Treatment of Huntington’s Disease – Randomized Phase. EudraCT: 2007-004988-22.
mMS	Modified Motor Score
mPPT	Modified Physical Performance Test
MTD	Maximal Tolerated Dose
PBA-s	Problem Behaviors Assessment – Short Form
PDF	Portable Document Format
PET	Positron Emission Tomography

PK	Pharmacokinetics
PM	Poor Metabolizers
PRIDE-HD	A Phase 2, Dose-finding, Randomized, Parallel-group, Double-Blind, Placebo-controlled Study, Evaluating the Safety and Efficacy of Pridopidine 45 mg, 67.5 mg, 90 mg, and 112.5 mg Twice-Daily Versus Placebo for Symptomatic Treatment in Patients with Huntington's Disease (TV7820-CNS-20002) EudraCT: 2013-001888-23; IND 77,419
qD	Once Daily
QTcF	QT Interval Corrected for Heart Rate using Fredericia's Formula
REB	Research Ethics Board
RV	Remote Visit
RV1	First remote visit
S1R	Sigma-1 Receptor
SAE	Serious Adverse Event
TC	Telephone Contact
TFC	Total Functional Capacity
UHDRS	Unified Huntington's Disease Rating Scale
UHDRS-TMS	Unified Huntington's Disease Rating Scale-Total Motor Score
UID	Unique Identification
US/USA	United States of America
USV	Unscheduled Visit
VTV	Virtual Transition Visit

## 2 BACKGROUND AND RATIONALE

### 2.1 Background

Huntington's disease (HD) is a fatal neurodegenerative disorder with an autosomal dominant mode of inheritance (Quinn and Schrag 1998). HD is caused by a cytosine-adenine-guanine triplet repeat expansion in the huntingtin gene (HTT), which results in an expanded polyglutamine stretch in the HTT protein (Huntington's Disease Collaborative Research Group 1993).

HD is characterized by progressive cognitive decline, psychiatric and behavioral symptoms, and a movement disorder syndrome often including choreiform movements. The age of onset of the signs and symptoms of HD and the rate of disease progression can vary greatly. Adult onset HD most often begins between 30 and 40 years of age. The illness generally lasts 15 to 20 years and is fatal. Following diagnosis, motor and cognitive functions steadily decline, ultimately leading to a state of immobility, dementia, and premature death (Ross and Tabrizi 2011). Psychiatric and behavioral symptoms often start before the onset of motor symptoms, but may also develop with the progression of disease. Not all individuals with HD experience the same psychiatric symptoms, which commonly include anxiety, depression, obsessive-compulsive behaviors, and personality change. Patients with HD commit suicide 4 to 8 times more often than the general population (Farrer 1986, Schoenfeld et al 1984). All patients with HD also have progressive cognitive impairment that is often characterized by executive dysfunction, especially early in the disease, but other cognitive realms are also affected, including learning and memory, motor planning, processing speed, attention, visuospatial processing, timing, emotion processing, and working memory. Cognitive impairment is a major contributor to disability among patients with HD (Ross et al 2014) and is associated with meaningful decrement in functional capacity, driving proficiency, ability to conduct accustomed work, and quality of life (Paulsen and Long 2014).

Pridopidine (TV-7820; formerly ACR16 and ASP2314) is an investigational, oral small molecule in development for the treatment of HD under investigational new drug (IND) application 077419. Pridopidine has been granted orphan drug designation both in the US (12 December 2005, Orphan Designation No. 05-2139) and the European Union (EU/3/05/288) as a treatment for adults with HD. It was originally described as a dopamine stabilizer, with effects regulating dopamine-dependent behaviors.

[REDACTED]

[figure not shown]
[REDACTED]

[REDACTED] Low affinities of pridopidine were also found for several other central nervous system receptor targets (in addition to the D2R), including serotonin 5-HT1A, 5-HT2A, and 5-HT7, adrenergic alpha-1, alpha-2A, and alpha-2C, dopamine D3, muscarinic M2, and histamine H3 (Studies 942038, 942027, and DPR-2014-055), all in the micromolar range (similar to its affinity towards D2R). However, recent studies show that pridopidine has ~100-fold higher affinity for the sigma-1 receptor (S1R; IC50 ~ 100nM) (Sahlholm et al 2013; DPR-2014-055).

Receptor occupancy for the S1R and D2R has been evaluated using in vivo positron emission tomography (PET) imaging in the rat. The PET imaging confirmed that pridopidine occupies the S1R at low doses (≤15 mg/kg) and the D2R at higher doses (more than

[figure not shown]

15 mg/kg) (Sahlholm et al 2015). After assessing receptor occupancy using (i) known binding affinities of pridopidine to human and rodent S1R and D2R in vitro, (ii) in vivo PET imaging in rats, and (iii) the extensive pharmacokinetic (PK) profiling of pridopidine in the different species, the clinical dose of 45 mg twice daily (bid) is expected to occupy 60% to 85% of S1R and <30% of the D2R. It is speculated that at the low 45 mg bid dose, pridopidine's effect is mainly mediated by the S1R, while at higher doses a more complex activity of pridopidine is initiated by binding to additional low affinity receptors.

As of January 2017, over 1260 subjects (206 of which were healthy volunteers) have been exposed to various oral daily doses of pridopidine in completed and ongoing clinical studies. The majority of the safety database is composed of the HD patients from the HART, MermaiHD, and PRIDE-HD double-blind, placebo-controlled studies (and their corresponding extensions) who received various doses of pridopidine for varying durations for a total of 958.7 patient years.

An integrated safety analysis of the HART, MermaiHD, and PRIDE-HD studies was performed according to the 7 dose groups (placebo, 10 mg bid, 45 mg once daily (qd), 45 mg bid, 67.5 mg bid, 90 mg bid, and 112.5 mg bid) investigated in these studies. Based on the large safety database, the adverse event (AE) profile of pridopidine 45 mg bid is benign and comparable with placebo.

Thus, the 45 mg bid dose has a favorable safety and tolerability profile compatible with continuing development.

